**A PHASE I/II STUDY TO DETERMINE
THE SAFETY AND EFFICACY OF CURCUMIN
IN PATIENTS WITH ORAL MUCOSITIS
SECONDARY TO CHEMOTHERAPY**

Principal Investigator: [name]
Aurora BayCare Medical Center
[name]
[name]
[contact]
[contact]
Email: [contact]

Sub-investigators: [name]
[name]
[name]
[name], Pharm D, BCOP
[name]
[name]

Study Coordinators: [name]
[name]
[name]

Sponsor: Aurora Health Care
[name]
[name]

Protocol version: April 29, 2015

PRECIS

Background:

Oral mucositis is a common and often debilitating complication associated with cancer treatment. Treatment of mucositis is mainly supportive - oral hygiene is the means of treatment. Curcumin (Turmeric), a frequently-used spice in India and Southeast Asia, can reduce bacterial load and prevent inflammation in cultured epithelial cells and prevent chemotherapy- and radiotherapy-induced mucositis in animal models.

Objectives:

The primary objective of this Phase I/II study is to determine the maximum tolerated dose (MTD) of oral curcumin in patients who have chemotherapy-induced mucositis. The secondary objectives of this study are to determine whether oral curcumin:

1. Decreases an objective measurement of oral mucositis
2. Decreases the pain associated with oral mucositis
3. Decreases the duration of mucositis
4. Has an acceptable safety profile

Eligibility:

Inclusion Criteria:

- ≥ 18 years of age
- \geq grade 2 oral mucositis related to chemotherapy for cancer

Exclusion Criteria:

- Current use of therapeutic doses of anticoagulants such as warfarin or antiplatelet agents (prophylactic doses and agents are acceptable)
- Biliary tract obstruction or cholelithiasis

Design:

This is a phase I/II study involving 2 parts. The first part is a dose escalation to determine the maximum tolerated dose of curcumin. There will be 3 subjects at each dose level of curcumin and 4 dose levels of curcumin. Each dose will be given 3 times each day for 14 days. Each dose will be given as a mouth rinse containing curcumin and water. The mouth rinse will be used for 30 seconds and then swallowed. Subjects will be evaluated for dose-limiting toxicity until the MTD is determined.

The second part of the study is an expansion at the MTD. Subjects will be randomized 1:1 to an experimental arm (curcumin) and a control arm (standard of care), with 23 subjects enrolled to each arm. Subjects on the experimental arm will use a mouth rinse containing the MTD of curcumin 3 times each day for 14 days. Subjects on the control arm will use a standard mouth rinse 3 times each day for 14 days. Both mouth rinses will be used for 30 seconds and then swallowed. Subjects will be evaluated for response and toxicity. Statistical analysis of the response data will determine whether oral exposure to curcumin reduces mucositis.

Section	Contents	Page
1	1. BACKGROUND AND SIGNIFICANCE	4
2	OBJECTIVES / ENDPOINTS	5
3	STUDY DESIGN	5
4	SUBJECT SELECTION	6
4.1	INCLUSION CRITERIA	6
4.2	EXCLUSION CRITERIA	6
5	STUDY PROCEDURES AND SCHEDULE	6
5.1	STUDY VISITS	7
5.2	STUDY CALENDAR	10
5.3	PREPARATION OF STANDARD MOUTH RINSE	11
5.4	PREPARATION OF STUDY MOUTH RINSE (CURCUMIN)	11
5.5	STUDY DRUG (CURCUMIN) DOSE	11
5.6	DETERMINATION OF MTD	11
6	EXPECTED ADVERSE EVENTS	12
6.1	DOSE-LIMITING TOXICITY	12
6.2	CRITERIA FOR SUBJECT REMOVAL	12
6.3	CRITERIA FOR STUDY DISCONTINUATION	13
6.4	CRITERIA FOR DOSE REDUCTION	13
6.5	SERIOUS ADVERSE EVENTS (SAEs)	13
7	BENEFITS	13
8	SAMPLE SIZE	13
9	MEASUREMENT OF EFFECT	14
9.1	DETERMINATION OF OBJECTIVE MEASUREMENT OF ORAL MUCOSITIS	14
9.2	DETERMINATION OF SUBJECTIVE MEASUREMENT OF ORAL MUCOSITIS	14
9.3	DETERMINATION OF PAIN ASSOCIATED WITH ORAL MUCOSITIS	14
9.4	DETERMINATION OF DURATION OF MUCOSITIS	15
9.5	DETERMINATION OF TOXICITY PROFILE	15
9.6	CRITERIA TO BE EVALUABLE FOR EFFICACY AND SAFETY	15
10	CORRELATIVE STUDIES (LABORATORY STUDIES)	15
10.1	SAMPLE COLLECTION	15
10.2	EVALUATION OF PROINFLAMMATORY CYTOKINES	15
10.3	FUTURE RESEARCH AND SAMPLE DISPOSITION	16
11	DATA COLLECTION	16
12	MONITORING PLAN	16
13	REPORTING REQUIREMENTS	17
13.1	REPORTING REQUIREMENT FOR SERIOUS ADVERSE EVENTS (SAEs)	18
14	REGULATORY REQUIREMENTS	18
14.1	INFORMED CONSENT	18
14.2	INSTITUTIONAL REVIEW BOARD	19
14.3	SUBJECT CONFIDENTIALITY	19
15	EXPERIENCE OF THE INVESTIGATORS	20
16	REFERENCES	21

APPENDICES: A: DAILY LOG
B: HEALTH CARE PROVIDER ASSESSMENT TOOL
C: SUBJECT ASSESSMENT TOOL
D: BIOSKETCH FOR DR. [name]

1. Background and Significance

Oral mucositis refers to erythematous and ulcerative lesions of the oral mucosa observed in patients with cancer being treated with chemotherapy, and/or with radiation therapy to fields involving the oral cavity. Oral and/or GI mucositis has been reported in 51% of patients receiving chemotherapy for solid tumors or lymphoma[1]. Clinically significant oral mucositis has been reported in an even higher percentage (approximately 75–80%) of patients who receive high-dose chemotherapy prior to hematopoietic cell transplantation[2]. Lesions of oral mucositis are often very painful and compromise nutrition and oral hygiene as well as increase risk for local and systemic infection. In addition to reducing patients' quality of life, mucositis may act as a dose-limiting adverse event in chemotherapy and/or radiation therapy and thus, it requires attention and treatment in the oncologic setting[3].

The cause of oral mucositis induced by cancer treatment is believed to be due to the over-production of free radicals induced by the chemo- or radiotherapy, which damages cell DNA and further activates pro-inflammatory transcriptional factors such as NF- κ B. Activation of NF- κ B up-regulates inflammatory cytokines. The major inflammatory cytokines involved are IL-6, TNF- α and IL-1 β [4, 5].

Typically, patients undergoing chemotherapy for cancer begin to show symptoms of oral mucositis about four to five days after starting treatment. Symptoms are at their peak at around the tenth day, after which they slowly improve over the following few weeks. Patients undergoing radiotherapy generally develop symptoms at the end of the second week of treatment. The symptoms can last from six to eight weeks.

Although many prophylactic and supportive treatment options exist, including cryotherapy, palifermin, amifostine, intravenous glutamine, honey, topical oral antimicrobials[6] and Lactobacillus lozenges[7], there is little consensus for a stand-out treatment for breakthrough mucositis. Hundreds of institution-specific oral rinses known as “magic “ or “miracle” mouthwashes, that contain some combination of anticholinergic (i.e. diphenhydramine), anesthetic (i.e. viscous lidocaine), antacid (i.e. Maalox), coating agent (Sucralfate), anti-inflammatory (glucocorticoids), antifungal (Nystatin) and/or antibiotic (tetracycline or erythromycin) ingredients, are often used as first-line treatment[8] for breakthrough mucositis. One major issue regarding “magic” mouthwash formulations is a variance of institutional and literature standardization which inhibits the ability to accurately determine its overall efficacy in the treatment of chemotherapy and radiation-induced mucositis[9]. One controlled study to evaluate the efficacy of magic mouthwash showed no difference in efficacy among the common formulation and other treatment agents such as chlorhexidine and a simple saline/baking soda solution[10]. In addition, all these “magic mouthwashes” are formulated to provide symptomatic relief of the pain or to create a protective barrier to prevent and reduce the severity of oral mucositis caused by chemotherapy and /or radiation. However, these mouthwashes are generally not designed to target the inflammatory response associated with chemotherapy and /or radiation which cause the mucositis.

Curcumin (extracted from turmeric) is an herbal supplement that has an extensive

history of use in India and Asia for its potent anti-inflammatory action and lately is being investigated for use in treatments of rheumatoid arthritis, various cancers, and Alzheimer’s disease[11]. Curcumin has been shown to prevent chemotherapy- and radiotherapy-induced mucositis in animal models[12]. Two recent studies provide a basis for our current investigation. In the first study, Luer et al. demonstrated that curcumin reduced oropharyngeal bacterial load and prevented inflammation in cultured epithelial cells[13]. In a small pilot study of juvenile patients with chemotherapy-induced mucositis, topical curcumin was found to be safe and well-tolerated[14]. Curcumin’s anti-inflammatory and antibacterial action make it a viable and compelling option for chemotherapy-induced mucositis.

2. Objectives/Endpoints

The primary objective of this Phase I/II study is to determine the maximum tolerated dose (MTD) of oral curcumin in patients who have chemotherapy-induced mucositis. The secondary objectives of this study are to determine whether oral curcumin:

- Decreases an objective measurement of oral mucositis
- Decreases the pain associated with oral mucositis
- Decreases the duration of mucositis
- Has an acceptable safety profile.

3. Study Design

This is a phase I/II study involving 2 parts: a dose escalation part and an expansion at the maximum tolerated dose.

In the first part, there will be 3 subjects at each dose level of curcumin (see table below). The doses will be taken 3 times each day for 14 days. Each dose will be taken as a mouth rinse containing curcumin and water, 3 times each day for 14 days. The mouth rinse will be used for 30 seconds and then swallowed. Subjects will be evaluated for dose-limiting toxicity (DLT, defined in section 6.1). The maximum tolerated dose (MTD, defined in section 2) will be determined. Subjects may participate in the study at a higher dose level, after they have completed the study at the current dose level and if they are eligible.

# Subjects	Curcumin/dose (gram)	Curcumin/day (gram)
3	0.33	1
3	1.0	3
3	2.0	6
3	3.0	9

In the second part of the study, there will be 23 subjects enrolled to an experimental (curcumin) arm and 23 subjects enrolled to a control (standard of care) arm. Subjects will be randomized to take a mouth rinse with or without the MTD of curcumin, 3 times each day for 14 days. The rinses will be swallowed. Subjects will be evaluated for response and toxicity. Subjects in the first part of the study may participate in the second part of the study, if they are eligible.

In both parts of the study, if the mucositis score \leq Grade 2 but is unresolved after 14 days of taking the study mouth rinse (curcumin or control), then the subject will

continue to receive the study mouth rinse until the mucositis is resolved (Grade 0).

This study will involve 12 subjects in the first part, plus an additional 3 subjects if a dose-limiting toxicity occurs (see section 2) and 46 subjects in the second part for a total of 61 subjects. This study is expected to take 2 years to complete enrollment, treatment and follow-up (6 months for the first part and 18 months for the second part).

4. Subject Selection

Potential subjects will be identified and recruited from within the practice population of the investigators (including via referrals to the investigators from other physicians). Patients' medical charts may be reviewed to identify potential subjects and to help determine eligibility; a 502-A form is being submitted to allow this preparatory to research activity.

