5.6 Determination of MTD

The MTD will be determined as follows: If a DLT occurs in any one of the 3 patients at a specific dose level, an additional 3 patients must be treated at that dose level to achieve statistical validity of the MTD. If 2 of the 6 patients (17%) at a dose level develop a DLT, the previous dose level will be used as the MTD. If no DLT is observed, then the MTD will be the highest dose. To ensure safety of subjects at each dose level, all assessments will be completed at Visit 5 for subjects at a dose level before another subject is given study drug at the

subsequent dose level.

6. Expected Adverse Events

Toxicities will be graded by health care providers using the Common Terminology Criteria for Adverse Events (CTCAE) Version 4.0 weekly after initiation of study mouth rinse until mucositis is resolved (Grade 0) (see Provider Assessment in calendar, section 5.2). Toxicities will be assessed by subject self-evaluation during study mouth rinse administration between clinic visits (see Subject Assessment in calendar, section 5.2).

Very few studies have reported any severe or serious side effects from curcumin and most studies have involved oral administration of curcumin. No major toxicity has been found in studies where curcumin is used short-term. Increased bleeding may occur due to inhibition of platelet aggregation (very rare). Possible other side effects associated with curcumin include: vomiting, nausea, rash and GI distress. In a study of subjects with colon cancer, oral curcumin at doses ranging from 0.45 to 3.6 gram/day for 1 to 4 months was associated with nausea and diarrhea and caused an increase in serum alkaline phosphatase and lactate dehydrogenase[15]. In one study of patients with advanced pancreatic cancer, 5 of the 17 patients receiving oral curcumin (8 gram/day) in combination with gemcitabine reported intractable abdominal pain after a few days to 2 weeks of curcumin intake[16]. In a recent study of topical curcumin for mucositis in juveniles and children[14], there were no oral adverse events documented and no systemic adverse events that possibly could be related to the use of the curcumin mouthwash.

Patients will receive full supportive care as appropriate. The rationale for treatment, dosage and the date of treatment will be recorded in the medical record.

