6.1 Dose-limiting Toxicity

DLT resulting from any treatment component of the study will be defined in the list below. There will be no dose reductions in response to DLT.

- Any grade 2 or greater allergic response
- Any grade 3 or greater toxicity

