6.2 Criteria for Subject Removal

A subject will be removed from the study for the following reasons:

- Dose limiting toxicity.
- No improvement in mucositis after 14 days of taking the study mouth rinse.
- Patient decision to withdraw consent or discontinue the study.
- Deemed by the physician to be the best medical interest of the patient.
- At the discretion of the investigator, patients who are non-compliant.

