This study will involve 12 subjects in the first part, plus an additional 3 subjects if a dose-limiting toxicity occurs (see section 2). This sample size is similar to other phase I dose escalation studies and will result in a determination of maximum-tolerated dose. The first objective for the second part (n=46) is to determine whether curcumin decreases an objective measurement of oral mucositis. Mucositis assessment will be conducted by the provider using the WHO scale and CTCAE scale. The scales are continuous between 0 and 4. Analysis of variance will be used to compare the two groups of subjects (standard mouth rinse versus study mouth rinse) separately for each time period (baseline and each week after study mouth rinse initiation). In a one-way ANOVA study, sample sizes of 23, and 23 are obtained from the 2 groups whose means are to be compared. The total sample of 46 subjects achieves 91% power to detect differences among the means versus the alternative of equal means using an F test with a 0.05 significance level. The size of the variation in the means is represented by their standard deviation which is 0.50. The common standard deviation within a group is assumed to be 1.00.

9. Measurement of Effect

Differences between the two mouth rinse groups will be studied with the chi-square test for categorical factors and the analysis of variance F-test for continuous variables with a 0.05 significance level.

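### Dose levels may be filled by subjects who already tolerated a lower level, and section 5.6 counts them as if new, so the MTD can be pushed upward

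*Combined protocol and SAP*

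**What the plan says.** - **Re-entry within Part 1 (section 3).** "Subjects may participate in the study at a higher dose level, after they have completed the study at the current dose level". The sentence goes on to require that they are eligible.
- **Re-entry into Part 2 (section 3).** "Subjects in the first part of the study may participate in the second part of the study, if they are eligible". Eligibility is the only condition; having tolerated a Part 1 dose is not one.
- **Removal (section 6.2).** The first listed reason for removing a subject is "Dose limiting toxicity". Section 6.1 defines this to include "Any grade 3 or greater toxicity", arising from any treatment component.
- **Cohorts (section 3).** In Part 1, "there will be 3 subjects at each dose level of curcumin", over four levels. Nothing says that the three must be new.
- **Decision rule (section 5.6).** After one DLT in three, "an additional 3 patients must be treated at that dose level". Then: "If 2 of the 6 patients (17%) at a dose level develop a DLT, the previous dose level will be used as the MTD". (2 of 6 is 33%; the printed percentage does not affect this point.) Each level must finish Visit 5 before the next opens, so completers are available to return.
- **Chemotherapy (section 5).** Doses are adjusted in later cycles to reduce toxicity.
- **Size.** Section 8 says "This study will involve 12 subjects in the first part", plus 3 if a DLT occurs. Section 3 adds 46 for Part 2 and gives a total of 61.

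The exclusion criteria in section 4.2 do not bar earlier study curcumin. The documents give no washout, cap on re-entry, separate tabulation or repeated-measures method.

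**The concern.** The section 5.6 rule reads the DLT count at a level as evidence on how patients in general tolerate that dose. That reading is sound if the patients are unselected. Sections 3 and 6.2 together allow an upper-level cohort to consist partly or wholly of people who have already come through a lower level without a DLT. Their background toxicity may also be lower, because their chemotherapy may have been adjusted in the meantime and the DLT definition covers toxicity from any treatment component.

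Determining the MTD is the primary objective, and the dose so named goes to 23 randomised subjects in Part 2, who need not have been selected for tolerance. If the upper levels are cleared by selected people, that dose carries a higher DLT rate than Part 1 appeared to show.

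**Working it through.** **1. The plan's own figures.** 12 + 3 + 46 = 61, as stated. For Part 2, f = 0.50/1.00 and the noncentrality is 46 × 0.50² = 11.5. The noncentral F(1, 44) distribution at the 0.05 level gives power 0.912, so the stated 91% reproduces. Neither figure is wrong.

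**2. What 61 counts.** As written it is a sum of places. With no DLT, the 12 Part 1 places could be filled by as few as 3 people, and every Part 1 subject may go on to Part 2. Distinct people could therefore number anywhere from 46 to 61.

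**3. One level, fixed tolerance threshold.** Assumptions: each person has a fixed threshold (correlation 1), level 3 cleared with 0 DLTs in 3, and those three re-enter at level 4. Let p3 and p4 be the true DLT rates.

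- Rate at level 4 among level-3 tolerators: q = (p4 − p3)/(1 − p3).
- Level clears with new subjects: (1 − p4)³ + 3p4(1 − p4)² × (1 − p4)³.
- Level clears with three carried over: (1 − q)³ + 3q(1 − q)² × (1 − p4)³. Any expansion cohort must be new, because no level-3 tolerators are left.

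| p3, p4 | q | New subjects | Three carried over |
|---|---|---|---|
| 20%, 30% | 0.10/0.80 = 0.125 | 0.343 + 0.441 × 0.343 = 0.494 | 0.670 + 0.287 × 0.343 = 0.768 |
| 30%, 40% | 0.10/0.70 = 0.143 | 0.216 + 0.432 × 0.216 = 0.309 | 0.630 + 0.315 × 0.216 = 0.698 |

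**4. Whole escalation, correlation varied.** The section 5.6 rule was simulated with 20,000 runs per scenario. A subject has a DLT at level j if √ρ·u + √(1 − ρ)·e < Φ⁻¹(pj), where u is a standard normal value that stays with the person and e is drawn afresh at each treatment. Under re-entry, DLT-free subjects fill places first. Section 5.6 does not cover two or more DLTs in the first three; escalation was assumed to stop.

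Chance that the top level is declared the MTD:

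| Assumed true rates, levels 1–4 | New subjects | Re-entry, ρ = 0 | ρ = 0.5 | ρ = 0.9 |
|---|---|---|---|---|
| 5/10/20/35% | 25% | 25% | 38% | 50% |
| 10/20/35/50% | 4% | 4% | 13% | 24% |
| 15/25/35/45% | 5% | 4% | 15% | 29% |

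A second simulation of the first row gave about 25%, 37% and 49% for new subjects, ρ = 0.5 and ρ = 0.9. The new-subject figure also follows directly from the per-level clearing probabilities: 0.973 × 0.906 × 0.709 × 0.396 = 0.247. In the same row the observed DLT rate at the top level falls from 35% to 28% (ρ = 0.5) and 23% (ρ = 0.9).

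**The case against.** The strongest reply is that re-entry is a permission. A returning subject needs a further episode of grade 2 or worse mucositis and must pass every exclusion again, after chemotherapy has been adjusted to reduce toxicity. Re-entry could be rare. This stands: the size of the effect in practice is unknown, and the figures above are for maximal re-entry.

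Second, the bias depends on within-person correlation. A fixed threshold suits poorly a DLT defined as any grade 3 toxicity from any component in patients on changing chemotherapy. At correlation 0 the shift disappears, and cumulative toxicity could reverse it. This also stands, but at a correlation of 0.5 the shift is still material.

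Some stronger readings are tempting and are not supported:

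- *A level filled with carried-over subjects clears with probability 86% (or 83%).* This applies q to all six patients. Six level-3 tolerators cannot exist after a level that cleared. If level 3 had expanded and cleared with 1 DLT in 6, five would remain, giving at most 0.670 + 0.287 × (0.875² × 0.70) = 0.824 and 0.630 + 0.315 × (0.857² × 0.60) = 0.769.
- *The 61 are not distinct people.* The text shows only that they need not be.
- *The DLT counts within a level are not independent.* Nothing suggests that one person fills two places at the same level. The problem is selection between levels.
- *The Part 2 comparison is biased.* Allocation is randomised 1:1, so prior exposure balances in expectation. The 91% power reproduces, no analysis pools the two parts, and the objective mucositis score is given by clinic staff not affiliated with the study. What remains is modest: pain is self-reported, the two rinses differ in preparation, and section 11 lists medications within 30 days of screening but not prior study treatment as such.

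**Conclusion.** The point holds as a weakness in how the MTD is determined. Sections 3, 5.6 and 6.2, followed as written, allow upper-level DLT decisions to rest on subjects selected for tolerance. If tolerance is positively correlated within a person, that understates the DLT rate and can raise the declared MTD.

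Under the assumed 5/10/20/35% rates and maximal re-entry, the chance of declaring the top level rises by about 12 to 13 percentage points at correlation 0.5 and about 24 to 25 at correlation 0.9. With a fixed threshold and three carried-over subjects, level 4 clears with probability 77% against 49% for new subjects (20%/30% rates), or 70% against 31% (30%/40% rates). All DLT rates and correlations are assumptions, because the documents give none.

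A reader might conclude that the MTD will be overstated. The documents do not support that: the amount of re-entry is not specified, and the direction is likely rather than certain. The Part 2 overlap and the meaning of 61 are matters of clarity and reporting.

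**What to change.** - **Section 5.6:** base the 3- or 6-subject DLT decision at each level on subjects not previously treated with study curcumin. If re-entry is kept, tabulate DLTs in re-entrants separately, by level.
- **Section 3:** say whether 61 counts people or enrolments.
- **Part 2:** record prior study exposure, and report the comparison with and without Part 1 re-entrants as a sensitivity analysis.

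The stated sample size need not change, because the 12 + 3 places already allow for new subjects. The cost is possibly slower Part 1 accrual. The plan's own pace gives some reassurance: 46 subjects in 18 months is about 2.6 a month, and 12 to 15 new subjects in 6 months is 2.0 to 2.5 a month. That comparison is of averages only. Since each level waits for Visit 5 (about day 21), four levels in sequence need at least 4 × 3 = 12 weeks of follow-up, so some slippage is possible. Re-entrants face the same wait and must also develop eligible mucositis again.
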